AAT/tDCS sessions of personal combined-cue exposure, with follow-up assessments of cig/day, intent and confidence to quit at 1 week and 1-month post-training.

Our specific goals are:

Aim 1: Determine the effectiveness of AAT and tDCS to attenuate cue-induced

craving and attentional bias to personal smoking stimuli. AAT, tDCS, and combined AAT + tDCS will each lead to greater reductions in pre-post training cue-induced craving and improved behavioral (quicker reaction time) and neurophysiological (lower P300 ERP) measures of attentional bias for smoking cues over the control condition.

Aim 2: Determine the effectiveness of AAT and tDCS to reduce cue-provoked smoking behavior and daily smoking, and to increase intent and confidence to quit. AAT, tDCS, and combined AAT + tDCS will

each lead to greater pre-post-training reductions in smoking topography measures (latency to light & puff volume) assessed during cue exposure, as well as reduced cigs/day and increased confidence and intent to quit from pre-training to post-training and 1-week & 1-month follow-up over the control condition.

Aim 3: Examine if changes in reactivity to smoking-related cues (Aim 1) are associated with posttraining reductions in smoking topography and/or cig/day and increases in intent and confidence to quit. (Aim 2). Reduced craving and attentional bias to smoking stimuli across all groups will be associated with reductions in smoking topography post-training, as well as post-training and follow-up changes in cigs/day and confidence and intent to quit Secondary Aim: Explore sex and other individual differences as moderators of outcome measures to explore who might benefit most from AAT and tDCS methods.

There have been few recent innovative approaches for alleviating cue-induced craving to smoke. AAT and tDCS are two promising methods to newly apply to this endeavor. Although this exploratory work is not fully powered to detect significant interaction effects of AAT and tDCS, we will examine the size of the interaction to inform potential efficacy trials of combined AAT + tDCS vs the individual therapies alone. The results here will thus guide a future RCT of novel CET methodology within a cessation trial aimed at helping more smokers stay quit.

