*** Identify the subgroups and provide a justification:**

Children, individuals defined as under the age of 18, will not be included as it is illegal to sell cigarettes to minors in Pennsylvania. The safety and efficacy of tDCS has not been tested in pediatric smokers, and standard doses have not been established.

8. Describe the power analysis used and cite your method of statistical analysis.

If a power analysis is not possible, thoroughly justify the sample size required for the study, including appropriate literature citation (alternatively provide page reference in attached protocol):

Statistical design and power

This study uses a 2 x 2 AAT (AAT, active control[AC]) x tDCS (tDCS, sham tDCS) design to assess prepost training changes in cue-induced craving and smoking

topography (latency to light and puff volume during cue exposure) and attentional bias (reaction time and ERPs) to smoking-related cues, as well as daily smoking (cigarettes per day) and confidence and intent to quit. The primary analyses (Aims 1 and 2) will be evaluated via repeated measures multivariate analysis of covariance (RM-ANCOVA) and will test the main effects of AAT, tDCS, and their interaction on measures of craving, reaction time, P300 amplitude, controlling for baseline levels as covariates (Aim 1). This process will be repeated for Aim 2, where MANCOVA will test effects on latency to smoke, total puff volume, and cigs/day. An additional 2x2x3 repeated measures (RM-) MANCOVA will test group differences in cig/day and intent & confidence to quit

across time points (post-training, 1-week, and 1-month). For Aim 3, regression analysis will be used to examine if attenuation of cue-induced craving and attentional bias measures predict reductions in smoking topography and daily smoking and elevations in intention to quit and confidence to quit, while controlling for baseline levels of these variables. Exploratory analyses will probe whether sex and other individual differences (e.g., age, FTND) moderate the effects of AAT/tDCS training on all outcome variables.

Power is based on n=20 high treatment-interest smokers per group, with 4 experimental groups. Drop outs

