in this experimental study will be replaced. We will examine differential group dropout to assess tolerability of methods. Limited past work leads us to constrain our power analysis to AAT and/or tDCS for each variable, but we expect the synergistic effects of combined AAT + tDCS to be even greater, making these power analyses conservative. However, this exploratory work is not fully powered to detect significant interaction effects. Aim 1. Craving and Attentional bias. Assuming a Cohen's d effect size (ES) of 1.02- 1.57 based on prior literature, a multivariate $\alpha = .05$, and an R2 of .3 from other covariates in the model, we expect to have greater than 0.99 power to detect main effects of tDCS on cue-induced craving. Boggio et al.⁴¹ found an ES of $d=1.13$ for reduction in cue-induced craving via tDCS. Our pilot P300 EEG data from our current study in smokers with schizophrenia shows ES of $d=1.3$. AAT work indicates post-training

attentional approach bias reductions to smoking cues of $d=1.2629$, thus we expect greater than .80 power to detect changes in attentional bias. Aim 2. Smoking topography and cig/day. Based on our past cue studies, smoking topography to multiple cues are of similar magnitude to cue-induced craving ($d=.90$). Further, past tDCS studies of daily smoking outcome show an ES of 0.58100. Thus, with a multivariate of $\alpha=.05$, 20 subjects per group, and an R2 of .3, we expect greater than 0.84 power to detect an effect of tDCS on smoking behavior in both the MANCOVA assessing immediate effects on smoking behavior and the RM-MANCOVA assessing longitudinal effects on cig/day and intent & confidence to quit. Again, tDCS

+ AAT should enhance effects. Aim 3. Smoking prediction. Assuming $\alpha=0.17$ (conservative adjustment for 3 outcome variables) and controlling for other variables contributing an R2 of .3, we will have power greater than .99 to detect an R2 of 0.2422 or larger, in the model predicting smoking topography and cig/day from cue-induced craving and attentional bias change scores.

Research Activities

1. * Provide a detailed description of all research activities (including screening and follow-up procedures) that will be performed for the purpose of this research study. This description of activities should be complete and of sufficient detail to permit an assessment of associated risks.

The PI, Co-I's and Research Coordinators will be responsible for carrying out all the research activities.

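### Aim 3 pools the four arms without specifying arm terms, so its slope mixes shared treatment effects with any within-arm link between cue reactivity and smoking

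*Combined protocol and SAP*

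**What the plan says.** In Study Aims, item 1, the Aim 3 hypothesis is "Reduced craving and attentional bias to smoking stimuli across all groups will be associated with reductions in smoking topography", and it extends to cigarettes per day and to intent and confidence to quit.

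The model is in Study Design, item 8: "For Aim 3, regression analysis will be used to examine if attenuation of cue-induced craving and attentional bias measures predict reductions in smoking topography", with the adjustment given as "while controlling for baseline levels of these variables". The same paragraph names AAT, tDCS and their interaction for the Aim 1 and 2 models, but names none of them for Aim 3. No within-arm analysis or mediation model is described. The Aim 3 power text allows for other variables that contribute an R2 of .3, without saying what they are.

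The treatment hypotheses sit beside this. Under Aim 1, AAT, tDCS and the combination will "each lead to greater reductions in pre-post training cue-induced craving". Under Aim 2 the same three will "each lead to greater pre-post-training reductions in smoking topography measures (latency to light & puff volume) assessed during cue exposure" and will lower cigarettes per day.

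**The concern.** If a randomised factor lowers both craving and smoking, the arms that received it have lower means on both variables. A regression over all participants picks up that difference between arms as a slope. This happens even if, inside every arm, a participant's craving change says nothing about that participant's smoking change. The condition for it is what Aims 1 and 2 predict, so the better those aims do, the less the pooled Aim 3 slope can be read as information about craving and smoking themselves.

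What is at stake is interpretation. The Significance text argues that cue reactivity sustains smoking and that reducing it should help smokers quit, and the study is meant to guide a later trial. A significant pooled slope would naturally be read as support for that argument, although two parallel treatment effects could produce it.

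**Working it through.** **Inputs from the documents (Study Design, item 8).** "Power is based on n=20 high treatment-interest smokers per group, with 4 experimental groups", so N = 80. tDCS on craving: d = 1.02, the low end of the planning range of 1.02 to 1.57. tDCS on cigarettes per day: d = 0.58 (printed 0.58100; the trailing digits are probably a citation number). Aim 3 alpha is printed as 0.17 and described as an adjustment for three outcomes; 0.05/3 = 0.0167.

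**Assumptions.** Within-arm SD of each change score is 1. Within-arm correlation between craving change and smoking change is zero. Where baselines enter, they explain 30% of the within-arm variance of each variable. Craving is the only predictor unless stated.

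**1. The plan's own power figure.** For an R2 increment of 0.24 (printed 0.2422) with .3 from other variables:

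f2 = 0.24 / (1 - 0.30 - 0.24) = 0.24 / 0.46 = 0.522; lambda = 80 x 0.522 = 41.7.

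With three tested predictors, power is above 0.999 at alpha 0.17 and 0.9994 at 0.0167. The stated value of more than .99 reproduces.

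**2. Pooled correlation with no within-arm link.** A balanced 0/1 factor has variance 0.25, so one active factor gives

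r = 0.25 dc dy / sqrt[(v + 0.25 dc^2)(v + 0.25 dy^2)],

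where v is the within-arm variance left after baselines (1 without them, 0.7 with them) and t is approximately r sqrt(df) / sqrt(1 - r^2).

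- Without baselines: 0.25 x 1.02 x 0.58 = 0.1479; r = 0.1479 / sqrt(1.2601 x 1.0841) = 0.127; with df = 78, t is about 1.13.
- With baselines: r = 0.1479 / sqrt(0.9601 x 0.7841) = 0.170; with df = 76, t is about 1.51.

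Baseline adjustment removes within-arm noise but leaves the between-arm difference, so it raises the rate.

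**3. How often the slope is significant.** Simulation, 20 per arm, two-sided t test of the craving slope:

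| Scenario | Baselines | Arm terms | 0.05 | 0.0167 |
|---|---|---|---|---|
| tDCS only, 1.02 and 0.58 | no | no | about 20% | about 10% |
| tDCS only, 1.02 and 0.58 | yes | no | about 34% (repeat runs 32 to 34%) | about 20% (19 to 20%) |
| tDCS only, half size (0.51 and 0.29) | no or yes | no | about 6 to 8% | about 2 to 3% |
| tDCS moves craving, not smoking | no or yes | no | about 5% | about 1.5 to 2% |
| AAT assumed equal to tDCS | no | no | about 52% | about 34% |
| AAT assumed equal to tDCS | yes | no | about 76% | about 59% |
| Any of these | no or yes | yes | about 5% | about 1.7% |

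At the printed 0.17, the tDCS-only rate without baselines is about 41 to 42%, and about 17% once arm terms are added.

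**4. More than one predictor.** The plan also uses attentional-bias predictors. With craving at 1.13 and P300 at 1.3 both moved by tDCS, cigarettes per day at 0.58 and baselines included, a joint test of three predictors rejects 36% of the time at 0.05. With craving alone at 1.13 it rejects 37%. Adding predictors does not remove the effect.

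**5. Cost of arm terms.** With three more model terms and a within-arm increment of 0.24, power is still 0.9994 at 0.0167.

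**The case against.** The strongest reply is that Aim 3 speaks of association and prediction, not mediation. A pooled association is a legitimate quantity and it is the one stated. If treatment moves both variables, that association truly is non-zero, and detecting it is no error. This stands. The rates above are false positives only for a within-arm link, which the plan does not state as its hypothesis.

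Three stronger readings are tempting, and the documents do not support them.

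- *The model excludes arm.* A reader might infer this from the silence. The other variables in the power text are unnamed and could include arm, and the phrase about all groups could loosely mean within each group. What can be said is that arm terms are not specified, although they are specified for Aims 1 and 2.
- *A treatment that works is enough to make Aim 3 positive.* With the plan's tDCS effects alone, the pooled slope is non-significant at 0.05 in about two thirds to four fifths of trials. At half-size effects the excess is small. If treatment moves craving but not smoking there is none.
- *Rates above one half follow from the plan's figures.* They need AAT to match tDCS on craving and cigarettes per day. The documents give an AAT effect size only for attentional approach bias, and the Significance text says AAT has not been tested for reducing cue-induced craving.

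The 0.17 figures should not lead either: 0.17 is probably a decimal slip for 0.017, which is a separate matter.

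**Conclusion.** The point holds as one of specification and interpretation. As written, the pooled slope cannot separate a link between cue reactivity and smoking from two effects of the same treatment, so it cannot by itself support the rationale that reducing one reduces the other.

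The size is conditional. On the plan's tDCS effects, and with no within-arm link, the chance of a significant pooled slope is about four to seven times nominal at 0.05 (20/5 = 4; 34/5 = 6.8). It falls close to nominal at half those effects. The higher figure rests on the assumed 30% baseline share, and every figure rests on a unit within-arm SD. Aims 1 and 2 and the stated Aim 3 power are unaffected. This is a worthwhile, inexpensive improvement to a third aim in exploratory work.

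**What to change.** In Study Design, item 8, state that each Aim 3 regression includes AAT, tDCS and AAT x tDCS as covariates beside the baseline levels, and name the other variables assumed in the power text. Report the arm-adjusted slope next to the pooled slope, with confidence intervals for both. Keep the pooled slope as the answer to the association hypothesis as stated, and base any claim of a craving-smoking link beyond shared treatment effects on the arm-adjusted slope.

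The cost is a few sentences and about 3 degrees of freedom out of roughly 75. No new data, participants or procedures are needed.

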Study Design and Procedures. Eighty (male=40, female=40) high treatment-interest daily smokers age 26-55 will be recruited from the local Pittsburgh community. As noted, past work has not revealed sex differences in CR, AAT, or tDCS training outcomes with smokers, but we will examine sex differences here. Participants will be screened via telephone interview, and again in person, for multiple measures including level of quit interest, assessed by asking subjects if they intend to quit smoking in the next 1, 3, 6, 12 months, longer, or never. Using a 2 x 2 design we will examine AAT (AAT, active control [AC]) X tDCS (active, sham) to reduce cue-induced craving and smoking topography, and attenuate behavioral and neurophysiological measures of attentional bias to combined personal smoking cues. We will also determine the impact of this novel CET methodology on daily smoking, intent and confidence to quit, and explore sex and other individual differences in the efficacy. Eligible participants will come to the laboratory and complete informed consent and further screening, including vision screening for sensory deficits that may affect cue reactivity and/or EEG testing, re-assessment of treatment interest and completion of forms. Participants will also undergo the semi-structured interview to identify the places of which to take pictures, and complete camera practice. After initial screening, participants will be randomized to one of the 4 groups (stratified by sex & age). Dropouts will be replaced but examined by AAT/tDCS group to assess tolerability. Groups include: 1) AAT + active (2.0 mA) tDCS, 2) AAT + sham (0.01 mA), 3) active control (AC) + active tDCS, or 4) AC + sham. Participants will participate in AAT/tDCS intervention sessions for 5 days over 3 weeks, but the over all study will be 10 visits total similar to our tDCS/schizophrenia study (DA0417742), and that by Mattai et al. Cue-induced craving, smoking topography, and attentional bias (reaction time & ERPs), as well as cigs/day intent to quit90 and confidence in quitting91 will be assessed at Week 1 Baseline sessions 1 & 2 and Re-test sessions 9 & 10 during Week 3. Cigs/day, intent and confidence to quit will be re-assessed during follow-up phone calls 1-week and 1-month post-training

3. Describe the primary and secondary study endpoints:

Primary:

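### The AAT x tDCS interaction measures synergy, not the combination's advantage over each single therapy, and the two differences that do measure that advantage are not planned for reporting

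*Combined protocol and SAP*

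**What the plan says.** Study Aims, item 1, closing paragraph, concedes limited power for the interaction and then states that "we will examine the size of the interaction to inform potential efficacy trials of combined AAT + tDCS vs the individual therapies alone". The next sentence says that the results will guide a later randomised trial set within a cessation trial.

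Study Design, item 8 gives the analysis. The Aim 1 model "will test the main effects of AAT, tDCS, and their interaction on measures of craving, reaction time, P300 amplitude", adjusted for baseline, and the same approach is repeated for Aim 2. The power text adds that "this exploratory work is not fully powered to detect significant interaction effects". On sample size: "Power is based on n=20 high treatment-interest smokers per group, with 4 experimental groups". Dropouts "in this experimental study will be replaced".

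Aims 1 and 2 compare AAT, tDCS and the combination each with the control condition. The Innovation text in Study Aims, item 2, and Placebo Arm, item 4, speak in general terms of individual and combined impact; the latter sets this against a time and contact control. No section names AAT+tDCS minus AAT+sham, or AAT+tDCS minus AC+tDCS, as something to be estimated.

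**The concern.** The sentence in Study Aims pairs a quantity (the interaction) with a comparison (combination against each single therapy) to which it does not correspond. The interaction asks whether the combined effect exceeds the sum of the separate effects. A trial of the combination against a single therapy asks whether the combined arm does better than that single-therapy arm. The plan expects both therapies to work, and in that case the two answers differ.

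At stake is what this exploratory study passes on to the next trial. A reader handed an interaction near zero, or below it, could conclude that combining the therapies adds nothing when the combination is in fact better than either. The interaction is also estimated less precisely than either difference.

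**Working it through.** **Inputs.** From Study Design, item 8: 20 per arm, four arms, multivariate alpha .05, "an R2 of .3 from other covariates in the model", and d = 0.58 for tDCS on daily smoking. The 0.58 is followed in the text by digits that read as a citation number. Sidedness is not stated; two-sided is assumed. Dropouts are replaced, so 20 per arm is used without reduction. Outcomes are scaled to SD 1 and signed so that positive means benefit. The residual SD is sqrt(1 - 0.3) = 0.837.

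**The plan's own power figures.** For a main effect, 40 are compared with 40: SE = 0.837 x sqrt(2/40) = 0.187.
- d = 0.58: 0.58/0.187 = 3.10, giving power 0.87 (0.86 with the t distribution on 75 df). The plan states more than 0.84.
- d = 1.02, the low end for craving: power above 0.999. The plan states more than 0.99.

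Both statements hold for the main effects.

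**Algebra.** Let a and t be the effects of AAT alone and tDCS alone against AC+sham, and I the interaction. Relative to AC+sham, the arm means are:
- AAT+sham: a
- AC+tDCS: t
- AAT+tDCS: a + t + I

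Hence:
- combination minus AAT alone = t + I
- combination minus tDCS alone = a + I
- interaction = combination - AAT alone - tDCS alone + control = I

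I equals one of the two differences only if the corresponding single-therapy effect is zero.

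**Size for daily smoking, t = 0.58.** The values of I are illustrative. The chance of a non-positive estimate uses the interaction SE derived below.

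| True I | Combination minus AAT alone (t + I) | Chance that the estimated interaction is zero or negative |
|---|---|---|
| 0.29 | 0.87 | 0.22 |
| 0 (additive) | 0.58 | 0.50 |
| -0.29 | 0.29 | 0.78 |
| -0.58 | 0 | 0.94 |

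The combination beats AAT alone for any I above -0.58. This comparison needs only the documents' tDCS figure.

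The gain over tDCS alone is a + I, and no AAT effect on daily smoking is given. Under additivity it is simply a: nothing if a = 0, and 0.58 SD if a is assumed equal to t. Under that last assumption, in 200,000 simulated trials the estimated interaction was zero or negative in 50%. In 47% it was zero or negative while the combination mean was better than both single-therapy means.

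**Precision** (t multiplier 1.99 on 75 df).
- Interaction: SE = 0.837 x sqrt(4/20) = 0.374; half-width 1.99 x 0.374 = 0.74 SD.
- Combination minus one single therapy: SE = 0.837 x sqrt(2/20) = 0.265; half-width 1.99 x 0.265 = 0.53 SD.
- With R2 = 0 the SEs are 0.447 and 0.316, so the ratio is unchanged.

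Power for a true difference of 0.58 between the combination and one single therapy is about 0.58. For an interaction of the same size it is about one third.

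**Availability.** The planned model contains both main effects and the interaction, so it determines all four adjusted arm means. The tDCS main effect, averaged over AAT and AC, is t + I/2, so combination minus AAT alone is that main effect plus I/2. Likewise, combination minus tDCS alone is the AAT main effect plus I/2.

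**The case against.** The strongest reply is that the sentence promises little. It says that the interaction will be examined to inform later trials. It sets no threshold, does not say that a null interaction means no gain, and does not call the interaction the planning effect. The following sentence lets the results as a whole guide the next trial. A reader might infer that the sponsor is committed to dropping the combination if the interaction is small, or to sizing the next trial on it. The documents do not support that inference.

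Three further points carry weight:
- The study's hypothesis is synergy, and the interaction is the natural measure of it. It also enters both differences, so it is incomplete for the stated purpose rather than irrelevant.
- The two differences follow from the planned model. To say that they cannot be obtained would be wrong: the gap is in what the plan commits to report, not in the design.
- The later trial is to sit within a cessation trial. If its endpoint is cessation, no contrast on the present outcomes sizes it directly.

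The admission of limited power does not answer the point. It concerns precision, and a larger sample would estimate the interaction better without turning it into the combined-versus-single difference.

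**Conclusion.** The concern holds as a mismatch between a named quantity and its stated use. The plan ties the interaction to a comparison that it does not measure, and no section plans to report the two differences that do measure it. Under additivity and the plan's d of 0.58, the interaction is 0 while the combination beats AAT alone by 0.58 SD. The interaction's half-width is about 0.74 SD, against 0.53 SD for each difference.

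These figures assume SD 1, a common residual variance, R2 of .3, 20 analysed per arm and two-sided 95% intervals. The gain over tDCS alone on daily smoking cannot be sized from the documents. Misreading is a risk, not a certainty. The design, the data and the planned main-effect tests are unaffected. The change should be made because it is cheap and bears on a stated purpose of the study.

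**What to change.** In the closing paragraph of Study Aims, item 1, and in Study Design, item 8, state along these lines:

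*For each outcome, the baseline-adjusted differences AAT+tDCS minus AAT+sham and AAT+tDCS minus AC+tDCS will be estimated from the planned models with 95% confidence intervals. These estimates, with their uncertainty, will inform trials of the combination against the single therapies. The interaction will be reported separately, with its 95% confidence interval, as the measure of synergy.*

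Do not add a rule that the smaller of the two differences becomes the planning effect. The two estimates share the combined arm (correlation 0.5). With equal true effects, their minimum is therefore low on average by 0.265 x sqrt(0.5/pi) = about 0.11 SD. Such a rule would also be undefined across the many outcomes.

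The cost is a short passage of text and two extra contrasts per outcome, to be labelled as exploratory estimates. No new data or participants are needed.
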